## Introduction

This study evaluates spatiotemporal interactions between electrode pairs in Argus II retinal prosthesis users to understand how stimulation delay and retinal distance influence visual perception. The primary aim is to investigate the number of phosphenes elicited by varying spatial offsets (dist\_ret) and temporal delays (abs\_delay) between electrode pairs. The analysis explores both the main effects of these variables and their interaction on phosphene perception. As a Basic Experimental Study Involving Humans (BESH), the focus is on understanding the mechanisms of prosthetic vision in controlled experimental settings rather than direct clinical outcomes.

## Study Design

- **Goal:** To measure the influence of spatiotemporal parameters on phosphene perception.
- **Hypothesis:** The number of phosphenes (num\_phosphenes) elicited by paired-electrode stimulation varies as a function of stimulation delay (abs\_delay) and retinal distance (dist\_ret), with the interaction of these variables hypothesized to modulate the response.
- **Approach:** Participants underwent paired-electrode stimulation while varying spatial offsets and temporal delays. A total of 35 conditions were tested, including combinations of delays (0 ms to 50 ms) and distances (proximal to distal electrodes). Stimulation protocols used single pulses on pairs of electrodes to probe responses at different time scales. Each participant's responses were recorded and analyzed for the number of phosphenes elicited under each condition.

## Analysis Framework

- A **linear mixed model (LMM)** was selected to account for the hierarchical structure of the data, with subject\_id modeled as a random factor to capture inter-subject variability. Fixed effects included abs\_delay, dist\_ret, and their interaction (abs\_delay:dist\_ret).
- This model allows for the evaluation of the main effects of stimulation delay and retinal distance, as well as their combined interaction, on phosphene perception.
- No formal power calculation was conducted due to the rarity of the clinical population; the study leveraged within-subject comparisons to maximize statistical power.

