(<https://doi.org/10.1038/s41598-019-45416-4>). However, it is not clear whether this model will generalize to more complex stimulation patterns. We hypothesize that the shape and number of percepts elicited by multi-electrode stimulation depends on the geometric arrangement of activated nerve fiber bundles in the retina. Our model predicts that subjects should see a single phosphene when two activated electrodes stimulate the same optic nerve fiber bundle, and two phosphenes when the two electrodes stimulate distinct nerve fiber bundle.

We further hypothesize that object recognition can be improved by a stimulation strategy that minimizes accidental stimulation of passing nerve fiber bundles in the retina. We will use our computational model to predict which electrodes should be activated to produce a desired percept, and test whether this optimized stimulation strategy can improve behavioral performance.

The purpose of this research is to further our understanding of the visual experience of Argus II users. Clinical experience with existing devices makes it clear that the provided artificial vision differs substantially from normal sight. In the research proposed here, we will combine human behavioral measurements and computational modeling to try to develop better stimulation protocols for retinal implants.

Procedures

Overview. Our experiments are designed to quantify the perceptual experiences of retinal prosthesis patients. We will produce visual percepts in patients either by directly stimulating electrodes (using FDA-approved pulse trains) or by asking them to view a computer or projector screen and using standard FDA-approved stimulation protocols (as is standard for their devices) to convert the computer or projector screen image into pulse trains on their electrodes. All stimulation protocols will be FDA-approved.

Our experiments will follow standard procedures for collecting behavioral data on retinal prosthesis patients. Testing will be carried out within the ophthalmology department of our participating sites, in the clinical testing suite of the ophthalmological surgeon who helped with recruiting the patient. Use of the suite will require the permission of the ophthalmological surgeon who aids with recruitment, and co-ordination with the administrative staff member responsible for managing the ophthalmology clinic.

Methods

Retinal prosthesis setup

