The setup for using the Argus II Retinal Prosthesis System (Second Sight Medical Products; Sylmar, CA) is shown in Figure 1 below. The system consists of a 6x10 microelectrode array implanted epiretinally in one eye of the patient, a pair of glasses with a small embedded camera, and a video processing unit (VPU). Stimuli are delivered to the retina as a series of electrical pulse trains (square-wave, charge-balanced) via the various electrodes in the array. The chip is powered wirelessly by the external VPU through magnetic induction. Safeguards to ensure only

FDA-approved stimuli are delivered exist in both software (in the VPU) and hardware form (in the electronics of the implant).

Figure 1: Argus II setup

The setup can be operated in two different modes:

- 1) 'Camera mode': Video captured by the camera on the glasses is sent to the VPU (attached figure, Panel A), which converts incoming frames into an FDA-approved stimulation protocol that is relayed wirelessly to the implant (Panel B). This is how patients use the device in everyday life.
- 2) 'Direct stimulation mode': An external computer is used to specify the pulse trains applied to each electrode (e.g., a 1s 10 Hz cathodic pulse train, with a current amplitude of 100 microAmps and a pulse width of 45 microseconds to Electrode 12) using Second Sight's software suite. Specified stimuli are then sent to the VPU for safety checking, and then delivered to the implant. This mode can only be used by researchers in behavioral experiments.

Stimuli

We will be using the prosthesis setup in both camera mode and direct stimulation mode.

Stimuli will be biphasic square-wave electrical pulses of a given pulse duration, amplitude, and inter-phase gap, or a train of pulses with a given frequency and stimulus duration. None of these stimuli will elicit emotional responses or be aversive in any way.

As mentioned above, the VPU contains software that makes sure that all pulse trains are within FDA-approved safety limits. For example, pulses must be charge-balanced (equal anodic/cathodic charge; so that there is no lasting residual net current in the tissue) and must

have a charge density below 35 microCoulombs/cm² (FDA specification thought to be safe for long-term stimulation).

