Subjects are encouraged to take breaks as often as needed (they may leave the testing room). We use various experimental techniques including: (1) Same-different – e.g. subjects are shown two percepts and are asked if they are the same or different. (2) Method of adjustment – e.g. subjects are asked to adjust a display/stimulation intensity until a percept is barely visible, (3) 2-alternative-forced choice – e.g. subjects will be presented with two stimuli and asked which of the two stimuli is brighter (4) Identification – subjects are asked to identify which letter was presented.

Data collection

At the participating sites, ophthalmological records showing the position of the implant in the eye (fundus photographs) and the height of the implant from the retinal surface (OCT) will be obtained to screen potential subjects. This is necessary because in a significant number of subjects the implant is poorly positioned and the patient will not be able to carry out the required behavioral tests. Prescreening avoids frustration on the part of the patient, and unnecessarily expense (since these patients are not local). If we choose not to enroll a patient or the patient decides not to enroll these data will be immediately destroyed.

Many individual differences in the quality of vision produced by these implants is likely due to the health of the individual retina and/or the location of the prosthetic implant. At the participating sites, fundus and OCT images will be used to estimate the retinal location of the implant. This extracted information will be shared with the coordinating site, which will use these values to inform their computational models.

In some cases, as well as measuring accuracy, we will also measure improvement with practice by repeating the same task across multiple sessions (up to 5 sessions, each carried out on different testing days).

Importantly, identifiable data is used only for recruiting and analyzing ophthalmic records of the patient at each participating site. Each participating site is already set up to store identifiable data of their respective patients. No identifiable patient data will be shared across sites.

The coordinating site will only have access to de-identifiable behavioral results that include phosphene drawings, brightness ratings, behavioral judgments, response times, etc.

Compensation

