## Sample Size and Statistical Methods

- **Sample Size:** The study included data from 1,485 trials across 6 subjects, representing a unique dataset of rare clinical cases.
- **Primary Statistical Test:** Coefficients were estimated using Restricted Maximum Likelihood (REML). Statistical significance was assessed with a pre-specified threshold of  $p < 0.05$ .
- **Adjustment for Multiple Comparisons:** No corrections were applied, as the analysis was limited to a small set of predictors.

- **Validation:** All analysis code was reviewed externally to ensure appropriate statistical methods and reproducibility.

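### The SAP model names subject_id as its only random factor and has no electrode-pair term; if pairs were repeated and differ, the dist_ret p-value is too small, and under some layouts so are the other two

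*SAP*

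**What the plan says.** The SAP, Analysis Framework, gives fixed effects for abs_delay, dist_ret and their product. It says that subject_id is "modeled as a random factor to capture inter-subject variability" and adds: "This model allows for the evaluation of the main effects of stimulation delay and retinal distance, as well as their combined interaction". It names no electrode-pair term. It does not say whether subject_id enters as an intercept only or also with a slope.

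On the design, the SAP (Study Design) says: "A total of 35 conditions were tested, including combinations of delays (0 ms to 50 ms) and distances (proximal to distal electrodes"). On volume, the SAP (Sample Size and Statistical Methods) says: "The study included data from 1,485 trials across 6 subjects". Estimation is by REML, with significance at p < 0.05. The visible text does not give the number of distinct pairs, the trials per pair, the number of levels of each factor, or whether each pair was tested at every delay.

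The protocol (Purpose, Hypotheses) expects that "the shape and number of percepts elicited by multi-electrode stimulation depends on the geometric arrangement of activated nerve fiber bundles in the retina", and predicts that "subjects should see a single phosphene when two activated electrodes stimulate the same optic nerve fiber bundle" and two phosphenes when the bundles are distinct. The implant is a "6x10 microelectrode array implanted epiretinally in one eye of the patient" (Methods, Retinal prosthesis setup), and "fundus and OCT images will be used to estimate the retinal location of the implant" (Data collection).

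**The concern.** No passage defines dist_ret. With one array in one eye and its position taken from images, however, each pair within a subject has one distance. dist_ret is then a property of the pair, and the information about its effect comes from comparing pairs, not single trials.

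The protocol's own hypothesis says that distance is not the whole story. Two pairs equally far apart can lie on the same bundle or on different ones, and the count of phosphenes, which is the primary outcome, should differ between them. Trials on the same pair would then resemble each other more than the model allows. Given the subject, the model treats them as independent, so it overstates the information on dist_ret.

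All three fixed effects belong to the stated hypothesis and are tested at p < 0.05 without multiplicity correction. An understated standard error feeds directly into the study's conclusions.

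**Working it through.** The documents give no power or error-rate figure to reproduce.

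**From the documents**
- Trials per subject: 1,485 / 6 = 247.5.
- Trials per subject and condition: 1,485 / (6 × 35) = 7.07.
- Possible pairs on 60 electrodes: 60 × 59 / 2 = 1,770. With about 248 trials per subject, repetition is therefore not forced.

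**Assumed, for illustration only**
- 6 subjects × 7 distances × 5 evenly spaced delays × 7 repeats = 1,470 trials.
- Trial SD 0.45, so s² = 0.2025. Pair SD ω = 0.10 or 0.20.
- Two-sided Wald z tests, no true effects, subject intercept only.

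Three layouts, with n trials per pair:
- (a) one pair per subject and distance, tested at all delays: n = 35, 42 pairs;
- (b) seven pairs per subject and distance, tested at all delays: n = 5, 294 pairs;
- (c) a different pair in each delay-distance cell: n = 7, 210 pairs.

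**Formulas**
- Residual degrees of freedom: 1,470 − 6 − 3 = 1,461. Of these, d lie between pairs: (a) 42 − 6 − 1 = 35; (b) 294 − 6 − 1 = 287; (c) 210 − 6 − 3 = 201.
- Residual variance that the model estimates: E = s² + nω² × d / 1,461.
- Ratio of true to model-based variance:
  - dist_ret with centred delay, and all three terms in (c): (s² + nω²) / E.
  - dist_ret with uncentred delay in (a) and (b): here the coefficient is the effect at delay 0. The squared mean over the variance of delay is 25² / 312.5 = 2, so the ratio is (3s² + nω²) / 3E.
  - abs_delay and interaction in (a) and (b): s² / E.
- Type I error = 2 × (1 − Φ(1.96 / √ratio)).

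**Results at pair SD 0.10**
- (a) E = 0.2025 + 0.35 × 35 / 1,461 = 0.2109. dist_ret centred: 0.5525 / 0.2109 = 2.62, giving 23%. Uncentred: 0.9575 / 0.6327 = 1.51, giving 11%. Delay and interaction: 0.2025 / 0.2109 = 0.96, giving 4.5%.
- (b) E = 0.2025 + 0.05 × 287 / 1,461 = 0.2123. dist_ret centred: 0.2525 / 0.2123 = 1.19, giving 7%. Uncentred: 0.6575 / 0.6369 = 1.03, giving 5%.
- (c) E = 0.2025 + 0.07 × 201 / 1,461 = 0.2121. All three tests: 0.2725 / 0.2121 = 1.28, giving 8%.

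**Results at pair SD 0.20**
- (a) E = 0.2360. dist_ret centred: 1.6025 / 0.2360 = 6.79, giving 45%. Uncentred: 2.0075 / 0.7080 = 2.84, giving 24%. Delay and interaction: 0.86, giving about 3.5%.
- (b) E = 0.2418. dist_ret centred: 1.66, giving 13%. Uncentred: 1.11, giving 6%.
- (c) E = 0.2410. All three tests: 2.00, giving 17%.

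If no pair is repeated, or pair variance is zero, the rate is 5%.

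**A different assumed layout** (5 distances × 7 delays, pair intraclass correlation 0.05 to 0.3) gives the same directions:
- same pairs at all delays: dist_ret 5.7% to 40.8%, delay and interaction 2.0% to 4.6%;
- different pairs at different delays, each repeated: 5.8% to 24.4% for all three tests;
- pairs that also differ in their response to delay (intraclass correlation 0.1, slope SD 0.3): delay and interaction 5.5% to 9.6%, even with every pair at every delay.

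**Remedies for dist_ret when its effect varies between subjects.** Assumed: slope SD 0.03 phosphenes per distance step, pair SD 0.10, Wald z. Rates are uncentred / centred.

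| Layout | Pair intercept alone | Pair intercept and subject slope |
|---|---|---|
| (a) | 14% / 19% | 7% / 9% |
| (c) | 16% / about 32% | 7% / 10% |

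In (b), the pair intercept alone gives 20% / 34%, and a subject slope alone 7% / 10%. Most of what remains once a slope is in comes from using z with six subjects. With t on 5 df, a subject slope and no pair term, centred dist_ret falls to 5.0–5.2% in (a) and 3.7–5.1% in (b).

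**The case against.** The strongest reply is that no defect has been shown. It needs repeated pairs, pairs that differ at equal distance, and a subject intercept without slopes. No passage gives the first or the third, and the second comes from a hypothesis and not from data. This stands as a limit: the point is conditional. It does not remove it, because the model as written names no pair term, the study's own hypothesis predicts pair differences, and the sponsor holds the facts that settle the matter.

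Secondly, the size depends heavily on layout. With many pairs per distance and uncentred delay, the inflation is immaterial (5% to 6%). The large figures need one pair per subject and distance, which nothing in the SAP favours. This is correct.

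Thirdly, a subject slope for dist_ret may matter more than a pair term. For dist_ret this largely holds, and it is why the two belong together. A slope for dist_ret does nothing for abs_delay and the interaction when pairs change with delay: in (c) these stay at 8% / 17%.

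The external code review mentioned in the SAP does not supply the missing specification. The mechanistic (BESH) purpose does not exempt p-values that are used to test a stated hypothesis.

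**Conclusion.** The point holds in conditional form and should be acted on. If pairs were repeated and differ, a subject-intercept model understates the dist_ret p-value. The other two p-values are understated as well if different pairs served different delays or if pairs respond differently to delay. With constant pair differences and pairs crossed with delay, those two tests are slightly conservative instead (about 4.5% / 3.5% in layout (a)). The 5% to 45% range for dist_ret rests entirely on the assumed layout, standard deviations and z test. It is not an estimate for this study.

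A reader might infer more, and the documents do not support it:
- That the reported p-values are known to be wrong. Repetition of pairs is nowhere stated.
- That about 7 trials per subject and condition means 7 trials on one pair. A condition may have used several pairs.
- That the model has a subject intercept only. The SAP neither says so nor excludes a slope.
- That all three tests are inflated in every case. This depends on how pairs were combined with delays.

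**What to change.** Refit the collected trials with a random intercept for electrode pair nested within subject and a by-subject slope for dist_ret, both as parts of one model. The slope should not be a side check, since the pair intercept alone protects dist_ret poorly if the distance effect varies between subjects. Use a small-sample reference distribution for dist_ret, such as Satterthwaite or Kenward-Roger degrees of freedom, because there are only six subjects. Show this fit beside the specified one.

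Report distinct pairs per subject, trials per pair, whether pairs were crossed with delays, whether abs_delay was centred, and how subject_id enters the specified model. A pair intercept does not cover pairs that differ in their response to delay. If pairs were crossed with delays, say whether this was examined.

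The cost is two variance terms and a refit, using a pair identifier already needed to compute dist_ret. Intervals widen if pair variance is present (pair SD 0.10 / 0.20): for dist_ret in (a), about ×1.2 / ×1.7 uncentred and ×1.6 / ×2.6 centred; for all three terms in (c), ×1.13 / ×1.41. If pair variance is zero, the pair term changes them by about 4% or less. The slope adds 3% to 10% to the dist_ret interval when slope variance is zero. The small-sample correction can add up to 2.571 / 1.960 = ×1.31 if the degrees of freedom fall to 5.

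### The SAP reads main effects beside an interaction without stating centring or a marginal slope; entered as listed, the delay coefficient is the slope at zero retinal distance, which no electrode pair has

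*SAP*

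**What the plan says.** The SAP's Introduction sets the aim: "The analysis explores both the main effects of these variables and their interaction on phosphene perception". Study Design adds a directional role for the product term, "with the interaction of these variables hypothesized to modulate the response", and describes the conditions as "combinations of delays (0 ms to 50 ms) and distances (proximal to distal electrodes"), 35 in all, delivered to pairs of electrodes.

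Analysis Framework lists three fixed effects, `abs_delay`, `dist_ret` and `abs_delay:dist_ret`, with subject "modeled as a random factor to capture inter-subject variability". It then says "This model allows for the evaluation of the main effects of stimulation delay and retinal distance", together with their interaction.

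Under Sample Size and Statistical Methods, the primary test reads "Coefficients were estimated using Restricted Maximum Likelihood (REML"), and "Statistical significance was assessed with a pre-specified threshold of" p < 0.05. The same section reports that "The study included data from 1,485 trials across 6 subjects".

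The SAP text available for review names no centring, scaling, reference distance, marginal slope or simple slope.

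**The concern.** In a model with a product term, a lower-order coefficient is the slope of one variable where the other equals zero. Zero delay is a tested condition. Zero retinal distance is not, if `dist_ret` is the separation of two distinct electrodes, as the Introduction's description of spatial offsets between pairs suggests.

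A p-value reported as the main effect of delay could therefore test an extrapolation outside the experiment. If the hypothesised interaction exists, that test and a test of the average delay slope have different null hypotheses. A reader given only the coefficient and its p-value could not tell which question had been answered.

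**Working it through.** **No figure to reproduce.** The SAP gives no power calculation, effect size, variance or distance values. The algebra below is general, and the numbers illustrate it.

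**Algebra.** Let E[y] = b0 + b1·delay + b2·dist + b3·delay·dist.
- The delay slope at a given distance is b1 + b3·dist, so b1 is the slope at dist = 0.
- With distance centred at its mean m, the delay coefficient becomes b1c = b1 + b3·m. The interaction b3 does not change.
- By symmetry, b2 is the distance slope at 0 ms.

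**Check by REML on simulated data.**
- Inputs from the SAP: 1,485 trials, 6 subjects, 35 conditions.
- Assumed: 7 delays by 5 distances (1 to 5), residual SD 0.5, subject SD 0.2, true b1 = 0, true b3 = 0.003.
- Uncentred delay coefficient: 0.0001 (SE 0.0018, p = 0.94).
- Centred delay coefficient: 0.0093 (SE 0.0008, p < 1e-30).
- Identity: 0.00014 + 0.00308 × 2.99 = 0.0093.
- The interaction estimate and p-value are the same under both codings, and fitted values agree to rounding error.

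**Standard errors.** Take a balanced design with subject intercepts only, and let v be the variance of the tested distances. The centred delay coefficient and b3 are then uncorrelated, and Var(b3) = Var(b1c)/v. Hence Var(b1)/Var(b1c) = r = 1 + m²/v, which does not depend on the unit of distance.
- Assumed distances 1 to 7: m = 4, v = 4, r = 1 + 16/4 = 5, SE ratio √5 = 2.24.
- Assume also that the centred test has 80% power at two-sided 5% (noncentrality 2.802) and that there is no interaction. The uncentred noncentrality is 2.802/2.236 = 1.25, which gives 24% power.

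**With an interaction, same distances.** The uncentred noncentrality is 2.802 × (slope at 0 ÷ average slope)/2.236.

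| True delay slope | Slope at 0 ÷ average | Noncentrality | Uncentred rejects | Centred rejects |
|---|---|---|---|---|
| Proportional to distance | 0 | 0 | 5% | 80% |
| Proportional to distance minus 1 | −1/3 | −0.42 | 7%, of which 6% in the wrong direction | 80% |
| Falling to zero at distance 7 | 7/3 | 2.92 | 83% | 80% |

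If instead the average slope is zero and the interaction test has 80% power, the noncentrality is 2.802 × √((r − 1)/r) = 2.51 in absolute value. The uncentred test then rejects in 71%, and the centred test in 5%.

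**Sensitivity.** Let k be the between-subject variance of the delay slope divided by 6, relative to the centred residual sampling variance of the estimated average slope. The SE ratio becomes √((r + k)/(1 + k)). For distances 1 to 7 this is 1.73 at k = 1 (37% power) and 1.34 at k = 4 (55%), so the loss shrinks as subjects' delay slopes vary more.

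**When the fit is invariant.** A subject term u0 + u1·delay can be rewritten around a delay origin c as (u0 + c·u1) + u1·(delay − c). The new intercept and slope have a covariance that includes c·Var(u1). A model that allows correlated intercepts and slopes absorbs this. A model that forces them to be uncorrelated becomes a different model when delay is recentred, and the estimated interaction can move.

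**The case against.** The case on the other side has force on four counts.

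- **Coding is open.** A list of model terms does not fix the coding, and nothing in the SAP rules out centring. The model can yield an average delay slope, so the Analysis Framework sentence is not false. A reader might infer that the SAP has been shown to misreport a main effect. The documents do not support that: they are silent on coding, and silence is not an error.
- **The main question largely survives.** The Outcomes section defines the primary outcome as the phosphene count as a function of both variables, and the hypothesis concerns their interaction. Neither the fitted surface nor the interaction test depends on centring under the usual random-effect structures. What remains is narrower, but the SAP does claim main effects and applies a significance threshold to coefficients.
- **The sizes are illustrative.** A reader might infer that this study lost power. The distances, the 80% anchor and the slope patterns are all assumed, and in one pattern the uncentred test does slightly better.
- **Rejection with a zero average slope is not a false positive.** In that setting delay does affect the count at some distances. The rejection misleads only if it is read as an average effect, and the SAP does not say whether that is the intended quantity.

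The external review of analysis code reported in the SAP does not tell a reader which quantity was tested.

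**Conclusion.** The point stands as a cheap improvement. If the variables enter as listed, continuous and uncentred, and `dist_ret` is the inter-electrode distance, the `abs_delay` coefficient and its p-value refer to a condition that no electrode pair has. The `dist_ret` coefficient refers to 0 ms, which is tested, so it is interpretable but conditional. Given the hypothesised interaction, the delay coefficient can depart from the average slope either way.

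The identity follows from the algebra under those conditions. The 2.24-fold SE and the fall from 80% to 24% rest on assumed distances 1 to 7, subject intercepts only, balance and no interaction.

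The interaction test and fitted surface are unaffected with random intercepts only, or with correlated random intercepts and slopes. That does not hold in general with uncorrelated random slopes.

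**What to change.** State how both variables are coded and define the delay effect, in one of two ways:
- centre `abs_delay` and `dist_ret` at stated fixed values, for example the means over all analysed trials, before forming the product; or
- keep the fit and report the average delay slope over the tested distances, b1 + b3·m, with variance Var(b1) + m²·Var(b3) + 2m·Cov(b1, b3).

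In either case, give delay slopes with confidence intervals at the shortest and longest tested distances, and label the 0 ms distance slope as conditional.

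The cost is about one line of code and some SAP wording. The average slope depends on which conditions were tested, which is why the slopes at named distances should stand beside it. The data are already collected, so any recoding after an uncentred run should be disclosed as post hoc, with both sets of coefficients shown.

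### If retinal distances and delay effects both differed between the six patients, the SAP's raw delay-by-distance product would mix within- and between-patient information; distance should be split before the interaction is tested

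*SAP*

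**What the plan says.** The SAP's Study Design section hypothesises that the phosphene count depends on delay and on retinal distance, and that the two interact. Of the design it says "A total of 35 conditions were tested", with delays between 0 and 50 ms, and then "Each participant's responses were recorded and analyzed for the number of phosphenes elicited under each condition". It gives neither the distance levels nor the distances used in each patient.

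The Analysis Framework section enters `abs_delay`, `dist_ret` and `abs_delay:dist_ret` as fixed effects, with `subject_id` "modeled as a random factor to capture inter-subject variability". It states: "This model allows for the evaluation of the main effects of stimulation delay and retinal distance, as well as their combined interaction". It does not mention centring, a split of distance into within- and between-patient parts, or random slopes. In place of a power calculation it says "the study leveraged within-subject comparisons to maximize statistical power".

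Under Sample Size and Statistical Methods: "The study included data from 1,485 trials across 6 subjects". The fit is by REML with a 0.05 threshold. No effect size or SD is given.

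**The concern.** A subject intercept absorbs one thing: a patient who reports more or fewer phosphenes overall. It does not absorb a difference between patients in how strongly delay acts. If such differences happen to line up with the distances at which patients were tested, the raw product picks them up, because delay multiplied by a patient's mean distance still varies within that patient.

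The interaction is part of the stated hypothesis. A patient tested at longer distances who also has a steeper delay effect could make delay and distance appear to interact within an eye. The opposite pattern could hide a real interaction. Neither is a within-subject comparison, and the between-patient part rests on only six points. The issue is what the coefficient estimates even for these six patients. It is separate from how far six patients can be generalised.

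**Working it through.** **Inputs.** From the SAP: 6 patients, 1,485 trials, 35 conditions, delays of 0 to 50 ms, the three fixed effects, REML, and a 0.05 threshold (taken as two-sided). Assumed, because the documents give no figures: the distance levels, residual SD 0.5, patient-intercept SD 0.3, the between-patient SD of the 0 to 50 ms delay effect (0.1, 0.2 or 0.3 phosphene), and rho, the between-patient share of the variance of retinal distance. The SAP has no calculation of its own to reproduce.

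**1. Trial counts.** 1,485/6 = 247.5; 1,485/35 = 42.43; 1,485/(6 × 35) = 7.07. The data are not exactly balanced, but about seven trials per patient and condition fits a nearly balanced crossed design.

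**2. Decomposition.** For a patient with mean distance m:

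delay × dist = delay × (dist − m) + delay × m

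The last term varies within the patient, so an intercept cannot remove it. With delay unrelated to distance within patients and an intercept only:

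raw product coefficient ≈ (1 − rho) × within-patient interaction + rho × between-patient association

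Grand-mean centring leaves this unchanged. The distance main effect is different. There the intercept reduces the weight on the between-patient part to about 0.25/(0.25 + 247.5 × 0.09) = 1.1%, where 0.25 = 0.5² and 0.09 = 0.3².

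**3. Check of the formula.** These are two simulated data sets with patient mean distances spread widely (between-patient share 48%), fitted by REML with a random intercept.

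- True within-patient interaction 0, between-patient trend +0.20. Split model: 0.013 within (p = 0.80), 0.205 between. Formula: 0.52 × 0.013 + 0.48 × 0.205 = 0.105. Raw product: 0.106 (p = 0.006).
- True within-patient interaction 0.20, between-patient trend −0.20. Split model: 0.213 within (p < 0.001), −0.210 between. Formula: 0.52 × 0.213 − 0.48 × 0.210 = 0.010. Raw product: 0.009 (p = 0.82).

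Over 600 runs of each pattern (mean-distance SD 0.7 half-ranges), the raw product was significant in 56% of runs in the first, against 6% with the split. In the second it was significant in 32%, against 97%.

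**4. False positives by chance alone.** Here there is no within-patient interaction and no systematic trend. Table: intercept only, raw product, 1,500 runs per cell, six delays by seven distances.

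| Delay-effect SD | rho 0.1 | rho 0.2 | rho 0.3 |
|---|---|---|---|
| 0.1 | 7% | 8% | 10% |
| 0.2 | 11% | 16% | 20% |
| 0.3 | 16% | 25% | 33% |

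At rho = 0 the rate is about 5%. With patient-centred distance it is 4 to 6% throughout.

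A grid of seven delays by five distances (35 conditions) gives similar figures at SD 0.2: about 9%, 13% and 19%, against 3 to 7% when centred. REML fits at SD 0.2 gave 9%, 13% and 23% (300 runs per cell) and 13%, 17% and 19% (250 runs per cell).

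Both conditions are needed. On the seven-by-five grid (600 runs per setting), identical distances with differing delay effects gave 3.8 to 6.5%. Differing distances with identical delay effects gave 4.7 to 5.8%.

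**5. What rho means.** With five distances from −1 to +1 in half-ranges, the within-patient variance is (1 + 0.25 + 0 + 0.25 + 1)/5 = 0.5. Then rho = 0.1 needs patient means with SD √(0.5 × 0.1/0.9) = 0.24, and rho = 0.3 needs √(0.5 × 0.3/0.7) = 0.46. These are 12% and 23% of the full tested range.

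**6. Adding a random delay slope.** REML, 250 runs per cell, Monte Carlo SE about 1.4 points at 5%, some convergence warnings. At SD 0.2 the rates fell from 13%, 17% and 19% to 7%, 7% and 4%. At SD 0.3 and rho 0.3 they fell from 36% to 5%. In the second data set of step 3, the slope moved the raw estimate from 0.009 to 0.178, against a true 0.20. The slope fit for the first data set did not converge and is not used.

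**7. Cost of splitting.** The interaction standard error rises by 1/√(1 − rho): 1/√0.9 = 1.05, 1/√0.8 = 1.12, 1/√0.7 = 1.20.

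**The case against.** A reader might infer that the six patients were tested at different distances, since 1,485 divides by neither 6 nor 35. The documents do not support that. The Study Design section speaks of one set of 35 conditions and of each participant's responses under each condition, and the Protocol (Retinal prosthesis setup) describes the same 6 × 10 array for all users. Indivisibility shows only unequal trial counts, which alone give almost no between-patient distance variance. On an assumed common grid of seven delays by five distances:

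- seven complete repeats (1,470 trials) plus 15 extra trials, all at the farthest distance in one patient: rho = 0.001;
- eight repeats (1,680) with 195 lost at random: mean rho 0.0004, maximum 0.002 in 2,000 draws;
- the farthest level missing entirely in three of the six patients: rho = 0.036.

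All lie below the 0.1 at which the tabulated inflation begins. At rho = 0.001 the test rejected in 4.0% of 250 runs. This objection stands: rho of 0.1 to 0.3 is an assumption.

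A reader might also infer an intercept-only model. The SAP says random factor and leaves slopes open. A delay slope would remove most of the chance inflation, so much of the figure reflects an unstated random-effects structure. That stands too. The slope does not fully separate the two parts under a systematic between-patient trend, although such a trend is a further assumption.

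The sentence on within-subject comparisons concerns power. It does not claim that the product coefficient is purely within-patient. The need to know which comparison the test makes remains.

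Finally, it can be said that deviations from each patient's own mean give the same physical separation different values in different patients. This does not defeat the split, because the slope is still per unit of physical distance.

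**Conclusion.** The point holds conditionally. As written, the interaction term is a within-patient quantity only if the distribution of retinal distance was the same in all patients, or if their delay effects were the same. The Protocol (Data collection) attributes many individual differences in the quality of vision to retinal health and implant location, so six equal delay effects would be surprising. Whether the distances differed is unknown.

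If both differed and only an intercept was fitted, a nominal 5% test would run at roughly 9 to 20% for rho of 0.1 to 0.3 at a delay-effect SD of 0.2, and a systematic between-patient trend could create or mask an interaction. These sizes rest wholly on assumed inputs and cannot be computed from the documents. There is no evidence that the reported interaction is wrong. This is an inexpensive improvement that should be made, not a demonstrated error.

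**What to change.** In the SAP's Analysis Framework section:

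1. Tabulate each patient's trial count and the mean and range of `dist_ret`. This one table shows whether the issue arises.
2. Split `dist_ret` into the patient mean and the deviation from it. Enter both as main effects, and enter `abs_delay` multiplied by each.
3. Judge the hypothesis on `abs_delay` × within-patient deviation, and report the between-patient product descriptively only.
4. State the random-effects structure, and include a by-subject delay slope where it can be fitted.

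The SAP is written in the past tense and the data are in hand, so show the planned raw-product result alongside.

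The cost is a wording change, a re-run on existing data, and the loss of precision in step 7 of the working. If the patients' distances match, the split leaves the interaction estimate and its standard error unchanged.
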